### 14.1.1 Primary Immunologic Endpoint

Myeloma reactive T-cells: Log transformations will be used to induce normality in quantitative measurements, and if still non-normal, then nonparametric tests will be used. The primary endpoint of log 10 peak change in tumor reactive T cells from baseline will be quantified. A secondary analysis of peak change in tumor reactive T cells will be done by comparing the proportions of patients who experience >10-fold increase in IFNy expression, using a chi-squared test. Peak immune response will be correlated with clinical response in an exploratory fashion to assess the relationship between immune response and clinical response.

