### 14. STATISTICAL CONSIDERATIONS

## 14.1 Study Design

The study is designed as a Phase II open label study of vaccination with DC/myeloma fusions/GM-CSF plus nivolumab therapy as part of treatment for patients with relapsed multiple myeloma. Patients meeting initial eligibility will undergo harvesting tumor cells and undergo vaccine production. During this period patients will receive an initial cycle of nivolumab and will then undergo a series of vaccinations on day 1 of cycles 1-3. 25 evaluable patients will be enrolled. Therapy with nivolumab will continue for three additional cycles. Based on a prior phase II study of vaccination of myeloma patients with the DC/MM fusion vaccine approximately 50% patients demonstrated a >10-fold increase in IFNy expression to the baseline. Therefore, the combination of vaccination and nivolumab will be considered promising if the study shows evidence of at least 75% patients with >10-fold increase in IFNy expression, and would not be considered promising if >10-fold increase is observed in 50% or less patients. With total n=25 patients, the combination will be considered promising for further study if 17 or more patients demonstrate significant immune response. This decision rule has a 0.1 (significance level) probability of accepting the combination for further study if the true underlying significant immune response is 50% and a 0.85 (power) probability of accepting the combination if the true underlying immune response is 75%. For the absolute increase in IFNy expression, with n=25 patients, we will have at least 90% power to detect an effect size of 0.66 (one-sided Wilcoxon rank sum test, significant level of 0.05), which corresponds to a 0.36 difference in log10 IFNy fold increase assuming a standard deviation of 0.54 or a 2.3 difference in IFNy expression fold increase assuming a standard deviation of 3.5. We estimate the median fold increase in IFNy expression of vaccination alone be 14 (DFCI trial 04098). Therefore, the fold-change that can be detected in the combination is at least 16.1.

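### Section 14.1 sets its only numeric efficacy cut-off on the >10-fold proportion, but 14.1.1 makes log10 peak change primary with no success criterion and that proportion a secondary chi-squared comparison with no stated comparator; 14.1 also names a two-sample test for a power figure that fits a one-sample one

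*Combined protocol and SAP*

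**What the plan says.** Section 14.1 (Study Design) describes a one-arm, open-label trial of 25 evaluable patients. It takes its reference from a prior vaccine study in which "approximately 50% patients demonstrated a >10-fold increase in IFNy expression to the baseline", sets 50% against 75%, and states the rule: "With total n=25 patients, the combination will be considered promising for further study if 17 or more patients demonstrate significant immune response". It attaches a significance level of 0.1 and power of 0.85 to that rule.

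The same section gives power of 90% or more for the continuous rise at n=25 and effect size 0.66, under a "one-sided Wilcoxon rank sum test" at level 0.05. It adds: "We estimate the median fold increase in IFNy expression of vaccination alone be 14", and concludes that "the fold-change that can be detected in the combination is at least 16.1".

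A later paragraph of 14.1 gives overall response rate (ORR) a one-sided 10% exact binomial test (0.15 v 0.35, 82% power, n=25) and regards 35% as justifying a larger trial. ORR is labelled secondary and no responder count is given.

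Section 14.1.1, headed Primary Immunologic Endpoint, says: "The primary endpoint of log 10 peak change in tumor reactive T cells from baseline will be quantified". It allows log transformation or nonparametric tests but gives no null value, reference or threshold. It then says: "A secondary analysis of peak change in tumor reactive T cells will be done by comparing the proportions of patients" with a rise above 10-fold, "using a chi-squared test". It does not mention 17 of 25.

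Section 1.2.1 puts T-cell expansion and the 3-fold and 10-fold percentages together under the primary endpoint and does not rank them.

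**The concern.** The measure that decides whether the combination goes forward is not the measure that the analysis section calls primary. The measure called primary has no criterion by which it could succeed or fail. After the data are in, a report could lead with either and cite the plan for it.

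The proportion also acquires a second test. Comparing proportions by chi-squared normally needs two groups, and this trial has one. Whichever reading is adopted at analysis, the resulting p-value is not the decision rule of 14.1 and could point the other way.

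The continuous power statement has a related problem. A rank sum test compares two independent samples. With 25 patients and no second sample planned, the stated power cannot be a property of the test named.

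**Working it through.** **1. The rule in 14.1.** Inputs from 14.1: n=25, cut-off 17, rates 0.50 and 0.75. With X binomial(25, p):

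- P(X≥17 | 0.50) = 0.0539
- P(X≥17 | 0.75) = 0.8506
- P(X≥16 | 0.50) = 0.1148

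The stated power of 0.85 reproduces. The stated 0.1 is a ceiling: 17 is the smallest cut-off that stays within it, and the attained level is 0.054.

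**2. The chi-squared of 14.1.1, read as a one-sample test against 50%.** The expected count is 12.5 and the standard deviation is √(25×0.5×0.5) = 2.5. Uncorrected z = (k−12.5)/2.5; with continuity correction z = (k−13)/2.5. The level is 0.1, the only one the plan sets for this proportion.

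| Responders k | Form | z | One-sided p | Two-sided p | Rule |
|---|---|---|---|---|---|
| 16 | uncorrected | 1.4 | **0.081** | 0.162 | not promising |
| 16 | corrected | 1.2 | 0.115 | 0.230 | not promising |
| 17 | uncorrected | 1.8 | 0.036 | 0.072 | promising |
| 17 | corrected | 1.6 | 0.055 | **0.110** | promising |

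Two of the eight p-values (bold) contradict the rule. The other two forms, one-sided corrected and two-sided uncorrected, agree with it at both counts. The plan does not say which form applies. Exactly 16 responders has probability 0.061 at a true 50% and 0.078 at a true 75%; exactly 17 has probability 0.124 at a true 75%.

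**3. The continuous power statement.** Inputs from 14.1: effect size 0.66 (0.36/0.54 = 0.667 on log10; 2.3/3.5 = 0.657 on the raw scale), one-sided 0.05, n=25.

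- *One-sample signed-rank.* Large-sample power is about that of a one-sample t test with n multiplied by 0.955 (the efficiency of the Wilcoxon test for normal data): 25×0.955 = 23.9, power 0.931. Simulation with normal data also gives 0.93. At the lowest possible efficiency, 0.864, the power is 0.906. The stated 90% or more reproduces.
- *Rank sum, as named.* This needs m comparators, and none is planned. For illustration m is set to the sizes of earlier vaccine groups in sections 2.2 and 2.3: 17, 24 and 36. Simulation with normal data gives about 0.64, 0.71 and 0.79. The figure for 17 moves between about 0.63 and 0.65 with the version of the test. None reaches 0.90.

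**4. The continuous reference.** The stated detectable fold-change of 16.1 does not follow from the plan's own inputs. Adding the raw difference gives 14 + 2.3 = 16.3. A difference of 0.36 on log10 is a ratio of 10^0.36 = 2.29, and 14 × 2.29 = 32.1.

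**5. An interval that matches the rule.** The exact (Clopper-Pearson) one-sided 90% lower bound is 53.3% at 17/25 and 49.2% at 16/25. It lies above 50% exactly when the rule says promising.

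**The case against.** The strongest reply is that nothing decisive is lost. Section 14.1.1 sits under 14.1, which supplies both the 50% reference and the 17/25 rule. The chi-squared is described as a further analysis of the same peak-change variable, not as a separate endpoint, and a one-sample chi-squared against 50% is a legitimate test. At 0.1 it agrees with the rule in most forms. All of this stands, and it limits the point to an ambiguity about what is primary and a possible conflict at 16 or 17 responders.

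It is also fair that 17/25 is not the plan's only criterion for going further. The ORR statement is a softer second one, though it is secondary and has no cut-off. Three power statements rest on n=25 (proportion, continuous rise and ORR), and the plan does not say which of them set the sample size.

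On the rank sum test, individual fold rises could in principle be compared with those of an earlier vaccine-alone group, so the name is not impossible in itself. But no such comparison is planned, 14.1 gives that group only as a median, and the stated power does not hold at the illustrative sizes. That the authors meant signed-rank is an inference from the arithmetic.

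A reader might infer that 17/25 would fail the chi-squared because 0.072 exceeds 0.05. The documents do not support this: the level set for this proportion is 0.1, and no 5% level is given for it.

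**Conclusion.** The inconsistency is real and should be fixed before analysis. The plan's one numeric efficacy cut-off is on the >10-fold proportion, while 14.1.1 gives primary status to a continuous change that has no null or success criterion, and section 1.2.1 does not settle which is meant. The chi-squared has no stated comparator. On its most natural reading it can contradict the rule at 16/25 (p=0.081) or at 17/25 (p=0.110), depending on an unstated choice of form.

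The continuous power is wrong as written for the test named and right for a one-sample signed-rank test (0.93), so the test appears misnamed. The rank sum figures rest on assumed comparator sizes and normal data.

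Two stronger conclusions are tempting and do not follow. The go/no-go is not invalid: the 17/25 rule keeps alpha 0.054 and power 0.851 whatever p-value is reported beside it. Nor is n=25 shown to be too small: the continuous power is met once the one-sample test is used.

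**What to change.** In 14.1.1:

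- Make the >10-fold proportion the primary analysis: a one-sample exact binomial test against 0.50, with success at 17 or more of 25.
- State the attained one-sided alpha of 0.054 and power of 0.85.
- Report the exact one-sided 90% lower bound with the estimate.
- Delete the chi-squared comparison.
- Make log10 peak change a supporting one-sample analysis.

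In 14.1, replace rank sum by signed-rank, and reconcile the continuous reference (16.1, against 16.3 or 32.1) before it is used. Align section 1.2.1 so that it names the same primary measure.

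The cost is wording only. The sample size, the 17/25 cut-off and the sampling schedule do not change.

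If the sponsor intends log10 change to be primary, 14.1.1 must state its null value, test and success threshold. The decision rule in 14.1 would then have to change with it, so that route is more than a wording repair.

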### 14.1.2 Secondary Immunologic Endpoints

Additional exploratory analyses will be conducted in a similar fashion to examine a number of secondary immunologic endpoints, including: myeloma specific T cells in the bone marrow, antigen specific reactivity by tetramer analysis, and quantification of T-cell subsets and PD-1 expressing lymphocytes by flow cytometry. In each case, log transformations will be considered to induce normality, and if still non-normal then nonparametric tests will be used. Profiles of these secondary immunologic endpoints will be described at each time point. The

correlation between the immune environment measures and the myeloma specific T-cell response will be assessed and reported using Spearman rank correlation at each time point.

#### 14.1.3 Duration of follow-up

Patients will be followed monthly for the first 6 months following the end of treatment and then every 3 months for 5 years to assess disease status.

### **15. PUBLICATION PLAN**

The results should be made public within 24 months of reaching the end of the study. The end of the study is the time point at which the last data items are to be reported, or after the outcome data are sufficiently mature for analysis, as defined in the section on Sample Size, Accrual Rate and Study Duration. If a report is planned to be published in a peer-reviewed journal, then that initial release may be an abstract that meets the requirements of the International Committee of Medical Journal Editors. A full report of the outcomes should be made public no later than three (3) years after the end of the study.

**APPENDIX A** **PERFORMANCE STATUS CRITERIA**

ECOG Performance Status Scale		Karnofsky Performance Scale	
Grade	Descriptions	Percent	Description
0	Normal activity. Fully active, able to carry on all pre-disease performance without restriction.	100	Normal, no complaints, no evidence of disease.
		90	Able to carry on normal activity; minor signs or symptoms of disease.
1	Symptoms, but ambulatory. Restricted in physically strenuous activity, but ambulatory and able to carry out work of a light or sedentary nature (e.g., light housework, office work).	80	Normal activity with effort; some signs or symptoms of disease.
		70	Cares for self, unable to carry on normal activity or to do active work.
2	In bed <50% of the time. Ambulatory and capable of all self-care, but unable to carry out any work activities. Up and about more than 50% of waking hours.	60	Requires occasional assistance, but is able to care for most of his/her needs.
		50	Requires considerable assistance and frequent medical care.
3	In bed >50% of the time. Capable of only limited self-care, confined to bed or chair more than 50% of waking hours.	40	Disabled, requires special care and assistance.
		30	Severely disabled, hospitalization indicated. Death not imminent.
4	100% bedridden. Completely disabled. Cannot carry on any self-care. Totally confined to bed or chair.	20	Very sick, hospitalization indicated. Death not imminent.
		10	Moribund, fatal processes progressing rapidly.
5	Dead.	0	Dead.

## APPENDIX B: DOSE MODIFICATIONS FOR NIVOLUMAB-RELATED AES

### GI Adverse Event Management Algorithm

[figure not shown]
Rule out non-inflammatory causes. If non-inflammatory cause is identified, treat accordingly and continue I-O therapy. Opiates/narcotics may mask symptoms of perforation. Infliximab should not be used in cases of perforation or sepsis.

Patients on IV steroids may be switched to an equivalent dose of oral corticosteroids (e.g. prednisone) at start of tapering or earlier, once sustained clinical improvement is observed. Lower bioavailability of oral corticosteroids should be taken into account when switching to the equivalent dose of oral corticosteroids.

### Renal Adverse Event Management Algorithm

[figure not shown]
Rule out non-inflammatory causes. If non-inflammatory cause, treat accordingly and continue I-O therapy.

Patients on IV steroids may be switched to an equivalent dose of oral corticosteroids (e.g. prednisone) at start of tapering or earlier, once sustained clinical improvement is observed. Lower bioavailability of oral corticosteroids should be taken into account when switching to the equivalent dose of oral corticosteroids.

## Pulmonary Adverse Event Management Algorithm

[figure not shown]
Rule out non-inflammatory causes. If non-inflammatory cause, treat accordingly and continue I-O therapy. Evaluate with imaging and pulmonary consultation.

Patients on IV steroids may be switched to an equivalent dose of oral corticosteroids (e.g. prednisone) at start of tapering or earlier, once sustained clinical improvement is observed. Lower bioavailability of oral corticosteroids should be taken into account when switching to the equivalent dose of oral corticosteroids

## Hepatic Adverse Event Management Algorithm

Rule out non-inflammatory causes. If non-inflammatory cause, treat accordingly and continue I-O therapy. Consider imaging for obstruction.

[figure not shown]

Patients on IV steroids may be switched to an equivalent dose of oral corticosteroids (e.g. prednisone) at start of tapering or earlier, once sustained clinical improvement is observed. Lower bioavailability of oral corticosteroids should be taken into account when switching to the equivalent dose of oral corticosteroids.

\*The recommended starting dose for grade 4 hepatitis is 2 mg/kg/day methylprednisolone IV.

## Endocrinopathy Adverse Event Management Algorithm

[figure not shown]
Rule out non-inflammatory causes. If non-inflammatory cause, treat accordingly and continue I-O therapy. Consider visual field testing, endocrinology consultation, and imaging.

Patients on IV steroids may be switched to an equivalent dose of oral corticosteroids (e.g. prednisone) at start of tapering or earlier, once sustained clinical improvement is observed. Lower bioavailability of oral corticosteroids should be taken into account when switching to the equivalent dose of oral corticosteroids.

## Skin Adverse Event Management Algorithm

Rule out non-inflammatory causes. If non-inflammatory cause, treat accordingly and continue I-O therapy.

[figure not shown]
Patients on IV steroids may be switched to an equivalent dose of oral corticosteroids (e.g. prednisone) at start of tapering or earlier, once sustained clinical improvement is observed. Lower bioavailability of oral corticosteroids should be taken into account when switching to the equivalent dose of oral corticosteroids.

\*Refer to NCI CTCAE v4 for term-specific grading criteria.

^If SJS/TEN is suspected, withhold I-O therapy and refer patient for specialized care for assessment and treatment. If SJS or TEN is diagnosed, permanently discontinue I-O therapy.

[figure not shown]
## Neurological Adverse Event Management Algorithm

Rule out non-inflammatory causes. If non-inflammatory cause, treat accordingly and continue I-O therapy.

Patients on IV steroids may be switched to an equivalent dose of oral corticosteroids (e.g. prednisone) at start of tapering or earlier, once sustained clinical improvement is observed. Lower bioavailability of oral corticosteroids should be taken into account when switching to the equivalent dose of oral corticosteroids.

## Myocarditis Adverse Event Management Algorithm

Patients on IV steroids may be switched to an equivalent dose of oral corticosteroids (eg, prednisone) at start of tapering or earlier, once sustained clinical improvement is observed. Lower bioavailability of oral corticosteroids should be taken into account when switching to the equivalent dose of oral corticosteroids.

Prophylactic antibiotics should be considered in the setting of ongoing immunosuppression.

ATG = anti-thymocyte globulin; BNP = B-type natriuretic peptide; ECG = electrocardiogram; IV = intravenous; MRI = magnetic resonance imaging

Adverse Reaction	Severity	Dose Delays
Other – excluding hematologic toxicities	Other Grade 3 adverse reaction: First occurrence	Withhold dose and resume when AE returns to Grade 0 or 1
	Recurrence of same grade 3 adverse reaction 	Permanently discontinue
	Life-threatening or Grade 4 adverse reaction	Permanently discontinue
	Requirement for 10 mg per day or greater prednisone or equivalent for more than 12 weeks	Permanently discontinue
	Persistent Grade 2 or 3 adverse reactions lasting 12 weeks or longer	Permanently discontinue

1. Laboratory abnormalities determined to be not clinically significant are not subject to this criteria, hematologic in nature or otherwise.
